#### **15.1.6.6. Alcohol Breath Test**

An alcohol breath test will be performed at the time point indicated in the Schedule of Assessments.

#### **15.1.6.7. Pregnancy Testing**

A urine pregnancy test will be performed at the time points indicated in the Schedule of Assessments for WOCBP only. If a urine test is positive, a serum test will be performed immediately for confirmation.

#### **15.1.6.8. Follicle-Stimulating Hormone Test**

Postmenopausal status will be confirmed and documented through confirmation of FSH levels ( $\geq 40$  IU/mL) at Screening for amenorrhoeic female patients, as applicable.

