16. Women of childbearing potential (WOCBP) must be non-pregnant and non-lactating, and must use an acceptable, highly effective double contraception or be abstinent from heterosexual intercourse from Screening until study completion, including the follow-up period (please see Section 10.4.3 for acceptable methods of contraception). WOCBP must have a negative pregnancy test at Screening and Day 1 and be willing to have additional pregnancy tests as required throughout the study. Women not of childbearing potential must be postmenopausal for  $\geq 12$  months or be surgically sterile, including a hysterectomy with retention of ovary function is permitted. Postmenopausal status will be confirmed through testing of FSH levels  $\geq 40$  IU/mL at Screening for amenorrhoeic female patients.
17. Male patients must be surgically sterile ( $> 30$  days since vasectomy with no viable sperm), abstinent, or if engaged in sexual relations with a WOCBP, the patient and his partner must be surgically sterile (e.g., tubal occlusion, hysterectomy, bilateral salpingectomy, bilateral oophorectomy) or using an acceptable, highly effective contraceptive method from Screening until study completion, including the follow-up period and an additional 12 weeks after the last dose (please see Section 10.4.3 for acceptable methods of contraception).
18. Males must not donate sperm for at least 90 days after the last dose of study drug.
19. Partners of male patients and female patients will report pregnancy occurring within 90 days from cessation of study medication.

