10. Concomitant medications include all medications taken 30 days prior to the Screening visit.
11. Adverse events include medical conditions such as infections (e.g., cellulitis and lymphangitis) starting or worsening after LYT-100 or placebo administration. All other medical conditions reported around Screening and Baseline prior to study treatment administration will be reported as pre-treatment AEs.
12. Not required for amenorrhoeic female patients (see below); if a urine pregnancy test is positive, it must be confirmed by a serum pregnancy test.
13. Amenorrhoeic female patients only; postmenopausal status will be confirmed through testing of FSH levels ( $\geq 40$  IU/mL).
14. Patients will provide blood samples at baseline (Day -1) for the determination of CYP1A2, CYP2C9, CYP2C19, and CYP2D6 genotyping – Sample to be obtained on Day -1 of the first period only. Patients are required to provide consent for genotyping.
15. Hematology includes complete blood count and differential.
16. Serum chemistry includes glucose, total protein, albumin, electrolytes (sodium, potassium, chloride, total CO2), calcium, phosphorus, magnesium, uric acid, bilirubin (total, direct), ALT or AST, alkaline phosphatase, creatinine, blood urea nitrogen, creatine phosphokinase (CPK). Liver Function Tests (LFTs) will be collected at each visit and includes bilirubin (total, direct), ALT or AST, and alkaline phosphatase.
17. Coagulation includes international normalized ratio (INR), prothrombin time and APTT.
18. Inflammatory markers include: G-CSF, MIG, FGF-2, IL-4, IL-10, lymphotoxin- $\alpha$ /TNF- $\beta$ , leptin, IL-6, IL-1 $\beta$ , TNF- $\alpha$ , TGF- $\beta$ 1, MMP-9, TIMP-1, MCP-1.
19. Patient completes the Patient Diary starting 1 week prior to each study visit and returns the diary at the end of the week while attending the study visit.
20. Relative limb volume is measured by perometry. Perometry is a non-invasive technique involving a Perometer (Pero-System), which uses infrared light to scan a limb and obtain measurements of the limb's circumference. The truncated cone tape measure method can be used as a backup if the Perometer is unavailable, or not working at time of the patient visit.

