  16. WOCBP must be non-pregnant and non-lactating, and must use an acceptable, highly effective double contraception or be abstinent from heterosexual intercourse from Screening until study completion, including the follow-up period (please see Section 10.4.3 for acceptable methods of contraception). WOCBP must have a negative pregnancy test at Screening and Day 1 and be willing to have additional pregnancy tests as required throughout the study. Women not of childbearing potential must be postmenopausal for  $\geq 12$  months or be surgically sterile, including a hysterectomy with retention of ovary function is permitted. Postmenopausal status will be confirmed through testing of FSH levels  $\geq 40$  IU/mL at Screening for amenorrhoeic female patients.
  17. Male patients must be surgically sterile ( $> 30$  days since vasectomy with no viable sperm), abstinent, or if engaged in sexual relations with a WOCBP, the patient and his partner must be surgically sterile (e.g., tubal occlusion, hysterectomy, bilateral salpingectomy, bilateral oophorectomy) or using an acceptable, highly effective contraceptive method from Screening until study completion, including the follow-up period and an additional 12 weeks after the last dose (please see Section 10.4.3 for acceptable methods of contraception).
  18. Males must not donate sperm for at least 90 days after the last dose of study drug.
  19. Partners of male patients and female patients will report pregnancy occurring within 90 days from cessation of study medication.

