#### **10.4.3. Contraception**

No estrogen preparations (e.g., oestradiol, ethinylloestradiol) are to be used throughout the trial for contraception, hormone replacement therapy, or menopausal replacement therapy.

Acceptable, highly effective double contraception is defined as a condom AND one other form of the following:

- Established hormonal contraception (oral contraceptive pills [OCPs], long-acting implantable hormones, injectable hormones) except for preparations containing oestradiol, ethinylloestradiol
- A vaginal ring or an intrauterine device (IUD)
- Documented evidence of surgical sterilization at least 6 months prior to Screening (e.g., tubal occlusion, hysterectomy, bilateral salpingectomy, or bilateral oophorectomy for women or vasectomy for men [with appropriate post-vasectomy documentation of the absence of sperm in semen] provided the male partner is a sole partner).

Women not of childbearing potential must be postmenopausal for  $\geq 12$  months. Postmenopausal status will be confirmed through testing of FSH levels  $\geq 40$  IU/mL at Screening for amenorrhoeic female patients. Females who are abstinent from heterosexual intercourse will also be eligible.

Periodic abstinence (e.g., calendar, ovulation, symptothermal, post-ovulation methods) and withdrawal are not considered highly effective methods of birth control. Patient complete abstinence for the duration of the study and for 1 month after the last study treatment is acceptable.

Female patients who are in same sex relationships are not required to use contraception.

Males must be surgically sterile ( $> 30$  days since vasectomy with no viable sperm), abstinent, or if engaged in sexual relations with a WOCBP, the patient and his partner must be surgically sterile (e.g., tubal occlusion, hysterectomy, bilateral salpingectomy, bilateral oophorectomy) or using an acceptable, highly effective contraceptive method from Screening until study completion, including the follow-up period. Acceptable methods of contraception include the use of condoms and the use of an effective contraceptive for the female partner that includes: OCPs, long-acting implantable hormones, injectable -hormones, a vaginal ring, or an IUD. Patients with same sex partners (abstinence from penile-vaginal intercourse) are eligible when this is their preferred and usual lifestyle.

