### 13.1. Screening (Visit 1), Day -28 to Day -2

Prior to enrolling in the study, and before performance of any procedures, potential patients will attend a Screening session at which time they will be provided with full information concerning details of the study assessments and procedures. They will also be provided with an Informed Consent Form (ICF). Prior to being asked to sign the ICF, patients will be given time to review study information and ask any questions.

After the consent form is signed, Screening assessments will be carried out as follows:

- Eligibility assessment
- Review of medications, medical/surgical history (including breast cancer, surgical, radiation, and chemotherapy history, and inclusion/exclusion criteria)
- Recording of demographic information
- 12-lead ECG (after patient has been resting in a supine position for at least 5 minutes and prior to blood draws and assessment of vital signs)
- Complete physical examination
- Vital signs (body temperature, heart rate [HR], blood pressure [BP], respiratory rate [RR])
- Height, weight, and BMI
- Pre-treatment AEs and concomitant medication, including name, indication, dose, route, start and end dates. Pre-treatment concomitant medication will include all medications 30 days prior to Screening visit
- Urine pregnancy test: Not required for amenorrhoeic female patients (see below); if a urine pregnancy test is positive, it must be confirmed by a serum pregnancy test
- FSH test: Amenorrhoeic female patients only; postmenopausal status will be confirmed through testing of FSH levels ( $\geq 40$  IU/mL)
- Blood hematology (complete blood counts and leukocyte differential counts)
- Serum chemistry: including glucose, total protein, albumin, electrolytes [sodium, potassium, chloride, total CO2], calcium, phosphorus, magnesium, uric acid, bilirubin (total, direct), ALT or AST, alkaline phosphatase (ALP), creatinine, blood urea nitrogen, and creatine phosphokinase (CPK). LFTs will be collected at each visit and includes bilirubin (total, direct), ALT or AST, and ALP
- Coagulation: INR, prothrombin time, activated partial thromboplastin time (APTT)
- Urinalysis (dipstick – microscopy if abnormal)
- Urine drug screen (including cotinine test) and alcohol breath test

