### **21.4.6. Other Safety Assessments**

Findings of the following assessments will be listed by patient:

- Medical history
- Pregnancy test/FSH test
- Urine drug screen (including Cotinine Test)/ alcohol breath test
- Physical examination
- Serology (HIV, Hepatitis B and C screen)

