## APPENDIX 1: Blood Volumes

**Table 11: Estimated Blood Volumes**

Test	Per Test Volume	Total Number of Samples	Total Volume
CYP1A2, CYP2C9, CYP2C19, and CYP2D6 genotyping	4 mL	1	4 mL
Pregnancy test and/or FSH (as applicable)	4 mL	1	4 mL
Hematology	3 mL	6	18 mL
Blood chemistry	5 mL	10	50 mL
Coagulation	4 mL	6	24 mL
PK	4 mL	8	32 mL
Fibrotic and inflammatory biomarkers	4 mL	5	20 mL
Overall Blood Volume Collected Per Patient			152 mL

Abbreviations: FSH = Follicle-stimulating hormone; PK = Pharmacokinetics.

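### The FSH limit for confirming postmenopausal status is written as at least 40 IU/mL in all six places, 1000 times the probably intended 40 mIU/mL

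*Combined protocol and SAP*

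**What the plan says.** Criterion 16 treats a woman as not of childbearing potential if she has been postmenopausal for at least 12 months or falls under the surgical route, "or be surgically sterile, including a hysterectomy with retention of ovary function is permitted" (Section 10.1). For amenorrhoeic women, the postmenopausal route has a laboratory step: FSH measured at Screening against a stated limit of at least 40.

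That limit appears in six places, always with the unit IU/mL:

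- Synopsis, inclusion criterion 16: "IU/mL at Screening for amenorrhoeic female patients".
- Table 5 (Schedule of Events), footnote 13: "confirmed through testing of FSH levels ( $\geq 40$ IU/mL".
- Section 10.1, inclusion criterion 16, which repeats the synopsis.
- Section 10.4.3 (Contraception), which adds abstinence as a further route: "IU/mL at Screening for amenorrhoeic female patients. Females who are abstinent from heterosexual intercourse will also be eligible".
- Section 13.1 (Screening visit): "FSH test: Amenorrhoeic female patients only; postmenopausal status will be confirmed through testing of FSH levels ( $\geq 40$ IU/mL".
- Section 15.1.6.8: "IU/mL) at Screening for amenorrhoeic female patients, as applicable".

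FSH is mentioned elsewhere without a limit or concentration unit. Appendix 1, Table 11 has a blood-volume line, "Pregnancy test and/or FSH (as applicable", and Section 21.4.6 includes "Pregnancy test/FSH test" among the results to be listed by patient.

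**The concern.** An FSH limit of 40 is normally expressed in mIU/mL, which is the same as IU/L. Written in IU/mL, the prefix is missing and the limit rises by three orders of magnitude. It is an operative threshold in an inclusion criterion: the protocol states that postmenopausal status will be confirmed by it.

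If the limit is applied as written and cannot be reached, the confirmation fails for every amenorrhoeic woman tested. The documents do not say how a woman below the limit is to be classified. A cautious site could treat her as being of childbearing potential and require a condom plus a second method under Section 10.4.3, which she may not need. A site that substitutes 40 mIU/mL on its own judgement is applying a limit that is not in the approved text. Section 9.1 admits only patients who meet all applicable inclusion criteria, and Section 27.2 requires deviations to be reported and included in the study report.

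**Working it through.** The plan shows no calculation behind the limit, so the check is a count of its occurrences, a unit conversion and a comparison with assumed FSH values.

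**Inputs**

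- Written limit: at least 40 IU/mL (the six places listed above).
- Probable intended limit: 40 mIU/mL. This is inferred; the documents do not state it.
- Serum FSH values: not in the documents. I assume 20 to 300 IU/L and stretch the maximum to 1,000 IU/L.

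**Step 1: consistency.** All six statements carry the same unit. No FSH limit appears in mIU/mL or IU/L, so no section offers a correct version to fall back on. Loss of a letter when the PDF was read is unlikely. It would have had to happen identically in six separate sections, while prefixes survive elsewhere, for example mmHg in inclusion criterion 10 and msec in exclusion criterion 18.

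**Step 2: conversion.**

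- Written: 40 IU/mL × 1000 mL/L = 40,000 IU/L.
- Probable: 40 mIU/mL = 0.04 IU/mL; 0.04 IU/mL × 1000 mL/L = 40 IU/L.
- Ratio: 40,000 / 40 = 1000.

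**Step 3: can the written limit be reached?** Share of limit = FSH / 40,000; shortfall = 40,000 / FSH.

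| Assumed FSH (IU/L) | Share of written limit | Shortfall |
|---|---|---|
| 20 | 0.05% | 2000-fold |
| 100 | 0.25% | 400-fold |
| 300 | 0.75% | 133-fold |
| 1,000 | 2.5% | 40-fold |

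The conclusion would change only if serum FSH could reach 40,000 IU/L, which is 40 times the stretched maximum.

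**Step 4: what depends on the limit.**

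- Confirmation of postmenopausal status in amenorrhoeic women (criterion 16) depends on it directly.
- The surgical-sterility, contraception and abstinence routes do not (Sections 10.1 and 10.4.3).
- Urine pregnancy testing is waived for amenorrhoeic women with no FSH condition attached (Table 5, footnote 12; Sections 13.1, 13.2, 13.7 and 13.11). The limit therefore does not decide that waiver. It does mean that FSH is the scheduled laboratory check on childbearing status for these women.
- No endpoint, analysis population or model uses FSH; Section 21.4.6 only lists the results.

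**The case against.** The strongest reply is that the documents do not themselves show an error. The six statements agree, and no FSH range or assay unit is given. Both the intended unit and the claim that the limit is out of reach rest on outside knowledge of serum FSH. This is true, and it is why the intended unit is called probable and the range is labelled an assumption. The margin is wide enough that the conclusion does not depend on the exact range. Agreement among six statements does not make an unreachable limit correct; it means that a site has no section to check it against.

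The second reply is that the consequences are slight. Nothing says that a woman below the limit is excluded, other routes to eligibility remain, and laboratories and sites will probably read the limit as 40 mIU/mL. Nor is a site confined to recording a failed confirmation or quietly changing the limit: it can ask the study monitor, whom Section 20.1 makes available for advice between visits. These points stand, and they hold the severity at minor. They do not rescue the text, because a threshold that works only once each site has corrected it or queried it is still wrong as written.

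It could also be noted that FSH is scheduled only once, with one sample in Table 11. That carries no weight either way, since a repeat test would face the same limit.

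**Conclusion.** The point holds, as a minor error. The unit, the count of six and the factor of 1000 are certain from the text. Two things are assumed: that 40 mIU/mL was meant, and that serum FSH stays far below 40,000 IU/L.

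Taken literally, FSH confirms no amenorrhoeic woman as postmenopausal. The harm would be limited to failed confirmations and possibly unneeded contraception for some women. How many of the approximately 50 patients would be affected cannot be stated, because the number of amenorrhoeic women is not given. If sites apply 40 mIU/mL, the remaining problem is a mismatch between the protocol and practice. The safety, efficacy and biomarker analyses are untouched.

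**What to change.** Confirm the unit in which the laboratory reports FSH. Then replace IU/mL with mIU/mL (= IU/L) in all six places: synopsis criterion 16, Table 5 footnote 13, Section 10.1 criterion 16, Section 10.4.3, Section 13.1 and Section 15.1.6.8. All six should change together, so that the amendment does not turn a consistent error into a contradiction.

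The cost is a text correction in the next amendment. No new test, visit or data is needed.

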#### **15.1.6.9. Genotyping**

CYP1A2, CYP2C9, CYP2C19, and CYP2D6 genotyping is conducted prior to study entry as indicated in the Schedule of Assessments; patients are required to provide consent for genotyping.

## 16. ADVERSE AND SERIOUS ADVERSE EVENTS

In this study, AEs will be reported for all patients from the time of consent until the completion of the follow-up/EOS visit. AEs reported prior to the first dose will be denoted as pre-treatment. SAEs will be reported for all patients (enrolled and not enrolled) from the time of consent. AEs reported from the time of consent to confinement on Day -1 will be recorded as pre-treatment AEs. Treatment-emergent AEs will be evaluated from the first administration of study drug until the EOS visit. AEs that are ongoing at the final onsite visit will be marked as Not Recovered/Not Resolved on the AE eCRF page (see Section 16.1.4).

All spontaneously volunteered and enquired for, as well as observed AEs, will be recorded in the patient's medical records and the eCRF.

Infection due to cellulitis and lymphangitis will be reported as an AE. When noted, the Australian Lymphology Association's Infection/ Cellulitis Form will also be completed (see Appendix 4).

### 16.1. Definition of Adverse Events

An AE is any event, side-effect, or other untoward medical occurrence that occurs in conjunction with the use of a medicinal product in humans, whether or not considered to have a causal relationship to this treatment. An AE can, therefore, be any unfavorable and unintended sign (that could include a clinically significant abnormal laboratory finding), symptom, or disease temporally associated with the use of a medicinal product, whether or not considered related to the medicinal product.

Events meeting the definition of an AE include:

- Exacerbation of a chronic or intermittent pre-existing condition including either an increase in frequency and/or intensity of the condition;
- New conditions detected or diagnosed after study drug administration that occur during the reporting periods, even though it may have been present prior to the start of the study;
- Signs, symptoms, or the clinical sequelae of a suspected interaction;
- Signs, symptoms, or the clinical sequelae of a suspected overdose of either study drug or concomitant medications (overdose per se will not be reported as an AE/SAE).

Events that do not meet the definition of an AE include:

- Medical or surgical procedure (e.g., endoscopy, appendectomy); the condition that leads to the procedure should be reported as an AE if it meets the criteria of an AE;
- Situations where an untoward medical occurrence did not occur (e.g., social and/or convenience admission to a hospital);
- Anticipated day-to-day fluctuations of pre-existing disease(s) or condition(s) present or detected at the start of the study that do not worsen.

If there is evidence of an AE through report or observation, the Investigator or designee will evaluate further and record the following information:

- Time of onset and resolution
- Severity
- Causality/relation to study treatment
- Action taken regarding study drug
- Outcome

#### 16.1.1. Severity of an Adverse Event

Severity of AEs will be graded by the Investigator using the National Cancer Institute Common Terminology Criteria for Adverse Events (NCI-CTCAE version 5.0) or as follows:

- **Mild (Grade 1):** A type of AE that is usually transient and may require only minimal treatment or therapeutic intervention. The event does not generally interfere with usual activities of daily living.
- **Moderate (Grade 2):** A type of AE that is usually alleviated with additional specific therapeutic intervention. The event interferes with usual activities of daily living, causing discomfort but poses no significant or permanent risk of harm to the research patient.
- **Severe (Grade 3):** A type of AE that interrupts usual activities of daily living, or significantly affects clinical status, or may require intensive therapeutic intervention.
- **Life-threatening (Grade 4):** A type of AE that places the patient at immediate risk of death.
- **Death (Grade 5):** Events that result in death.

#### 16.1.2. Causal Relationship of an Adverse Event

The Investigator will assess the relationship between study drug and the occurrence of each AE. The Investigator's assessment of the relationship of each AE to study drug will be recorded in the source documents and the eCRF. Alternative causes, such as medical history, concomitant therapy, other risk factors, and the temporal relationship of the event to the study drug should be considered and investigated, if appropriate. The following definitions are general guidelines to help assign grade of attribution:

- **Not related:** The event is clearly related to other factors such as the patient's environment or clinical state, therapeutic interventions or concomitant drugs administered to the patient. This is especially so when an event occurs prior to the commencement of treatment with the study drug.
- **Possible:** The event follows a reasonable temporal sequence from the time of study drug administration or follows a known response to the study drug but could have been produced by other factors such as the patient's clinical state, other therapeutic interventions, or concomitant drugs administered to the patient.
- **Probable:** The event follows a reasonable temporal sequence from the time of study drug administration and follows a known response to the study drug and cannot be

reasonably explained by other factors such as the patient's clinical state, other therapeutic interventions, or concomitant drugs administered to the patient.

